6.2 Survey instrument

Section X. Logistics and Network Measurement

Questions to be asked and/or filled in by enumerator.

X1	Fill in the name of the school	Name of school _____
X2	Fill in the ID of the school	School ID _____
X3	Ask student: What is your first name? Confirm with student that name was spelled correctly	Student first name _____
X4	Ask student: What is your last name? Confirm with student that name was spelled correctly	Student last name _____
X5	Enter ID of student from enrollment roster	Student ID _____
X6 (baseli ne AND endlin e!)	
Ask student: Now, I want to know who are the friends that you spend time with in your grade. I am going to read you the names of all students in your grade. For every name, I want you tell me if the student is a friend of yours that you spend time with.
 
[Prompt: Slowly read through enrollment list and prompt for answer at every name (pause, look, "is this a friend that you spend time with?"). Whenever student labels individual friend, put down number on the right.]
 
Protocol for AIR: At every school, obtain enrollment protocol from school officials. The protocol needs to be numbered such that every student has a unique ID. Each enumerator then gets one sheet. This requires making copies (by hand or electronically). AIR should write up a protocol on how this is undertaken.
	ID 1 _____ ID 2 _____ ID 3 _____ ID 4 _____ ID 5 _____ ID 6 _____ ID 7 _____ ID 8 _____ ID 9 _____ ID 10 _____ ID 11 _____ ID 12 _____ ID 13 _____ ID 14 _____

Section A. Demographic Characteristics

First, we have some general questions about your background.

A1	What day, month and year were you born?	Day	Month	Year
A2	What is your gender?	Male		
A3	What grade are you in?	Number	_____	
A4	What is your religion?	Islam		
		Catholic		
		Apostolic		
		Pentecostal		

		Anglican Christian, other Other Don't know
A5	What is your father's primary job?	Farmer ...
A6	Does your father have a hard time reading (e.g., a newspaper or a letter)?	Yes No
A7	Can your father write in English?	Yes No
A8	Are your parents married to each other?	Yes No
A9	What is your native language?	Nyanja Lozi Tonga Kaonde English Luvale Lunda Other Don't know

Section B: Knowledge about sexual and reproductive health				
Section B1: Family planning / contraceptives				
Now, we have some questions about contraception. By that we mean ways in which one can avoid getting pregnant.				
B1-1	Have you heard of family planning before?	Yes No		
	People have different opinions about cotraception. Do you think the following statements are true, false or do you not know?			
		True	False	Don't Know
B1-2	There are free contraceptives available in Zambia.	1	2	3
B1-3	Only married women are allowed to use contraceptives.	1	2	3

B1-4	Men have the right to determine when a woman should become pregnant.	1	2	3
B1-5	Women are very unlikely to get pregnant if the man correctly uses a condom.	1	2	3
B1-6	Women are very unlikely to get pregnant if the woman washes her vagina after having sexual intercourse.	1	2	3
B1-7	A woman is very unlikely to get pregnant the very first time she has sexual intercourse.	1	2	3
B1-8	It is recommended that all girls visit the health facility for yearly check-ups after they become sexually active.	1	2	3
	Next, we have some questions about particular family planning methods.			
B1-9	Do you know what an intrauterine device (IUD) is?	Yes → No B1-12		
	For the following two questions, please decide whether you think each statement is true or false or indicate that you don't know.			
		True	False	Don't Know
B1-10	IUD carries a risk of infertility	1	2	3
B1-11	IUD is a short-term method	1	2	3
B1-12	Do you know what an injectible contraceptive is?	Yes → No B1-15		
	For the following two questions, please decide whether you think each statement is true or false or indicate that you don't know.			
		True	False	Don't Know
B1-13	Injectables only last one month	1	2	3
B1-14	If you stop taking injectables, you still cannot get pregnant for at least a few months	1	2	3
B1-15	Do you know what birth control pills are?	Yes → No B2		

	For the following two questions, please decide whether you think each statement is true or false or indicate that you don't know.			
		True	False	Don't Know
B1-16	Women should take birth control pills every day	1	2	3
B1-17	If women miss just one or two birth control pills, it does not matter	1	2	3

	Section B2: Condoms Now, we are going to ask you a few questions about condoms.			
		True	False	Don't Know
B2-1	Condoms prevent women from getting pregnant.	1	2	3
B2-2	Condoms can be used more than once.	1	2	3
B2-3	Condoms prevent men and women from getting HIV/AIDS.	1	2	3
B2-4	Condoms prevent men and women from getting other sexual transmitted infections.	1	2	3
B2-5	Condoms are suitable only for steady relationships.	1	2	3
B2-6	If a girl wants to use a condom, that means she does not trust her partner.	1	2	3
B2-7	Condoms cannot help against sexually transmitted infections.	1	2	3

	Section B3: HIV and AIDS Now, we are going to ask you a few questions about HIV/AIDS.			
B3-1	Have you ever heard of HIV/AIDS?	Yes → B4		
	Please tell me whether you think the statement about HIV/AIDS is true, or false, or whether you don't know.			
		True	False	Don't Know

B3-2	You can see whether a person has HIV/AIDS.	1	2	3
B3-3	It is possible to cure AIDS.	1	2	3
B3-4	Sleeping with a virgin can cure AIDS.	1	2	3
B3-5	A mother can transmit HIV to her child when she is pregnant.	1	2	3
B3-6	You can get AIDS by sharing food with a person who has AIDS.	1	2	3
B3-7	You can get AIDS because of witchcraft.	1	2	3
B3-8	You cannot get HIV the first time you have sex.	1	2	3
B3-9	You can get HIV through kissing.	1	2	3
B3-10	A healthy person cannot get AIDS.	1	2	3
B3-11	AIDS can be transmitted by mosquitos.	1	2	3
B3-12	Everybody is going to get AIDS at some time in his or her life.	1	2	3

Section B4: Sexually transmitted infections (STIs)

Next, we want to ask you about sexually transmitted diseases other than HIV/AIDS.

B4-1	Have you ever heard about sexually transmitted diseases other than HIV/AIDS?	Yes No → C		
Please tell me whether you think the statement about sexually transmitted diseases is true, or false, or whether you don't know.				
		True	False	Don't know
B4-2	In Zambia, only sex workers have sexually transmitted diseases.	1	2	3
B4-3	You can always see if somebody has a sexually transmitted disease.	1	2	3
B4-4	Male circumcision reduces the risk of getting sexually transmitted diseases.	1	2	3
B4-5	Sexual transmitted diseases can cause infertility	1	2	3
B4-6	Sexually transmitted disease can never be cured.	1	2	3

	Please tell me whether you think it is true or false if a person can get tested for sexually transmitted diseases at the following places.			
		True	False	Don't Know
B4-7	Public clinic	1	2	3
B4-8	Private clinic	1	2	3
B4-9	In church	1	2	3
B4-10	Some NGO clinics	1	2	3
B4-11	Drug shop	1	2	3
B4-12	Gas station	1	2	3
B4-13	At the witch doctor	1	2	3

Section C: Self-reported behavior

Section C1: Sex

Now, we are going to ask you direct questions regarding your sexual experiences. If a question makes you feel uncomfortable, you can skip the question.

C1-1	In the last six months, did you visit a health clinic to talk about issues relating to sex or family planning?	Yes → C1-3 No
C1-2	When was that?	1 month ago 2 or 3 months ago 3-6 months ago 6-12 months ago More than 12 months ago
C1-3	In the past 6 months, have you been to the health facility as a patient?	Yes No
C1-4	(Only males) Are you circumcised?	Yes → C1-6 No
C1-5	When were you circumcised?	1 month ago 2 or 3 months ago 3-6 months ago 6-12 months ago More than 12 months ago
C1-6	Have you ever had sexual intercourse?	Yes → C1-8 No → C1-7

C1-7	What is the main reason that you have not had sex? → After, move to section C2.	No opportunity yet No sex before marriage Afraid of getting pregnant Afraid of getting diseases I want to be abstinent Don't know
C1-8	What was the main reason you have had sex?	Married Love Fun/curiosity Friend influenced me I received money in return I wanted to get pregnant I was forced Don't know
C1-9	How many sexual partners have you had in the last 12 months?	0 1 3-5 More than 5
C1-10	Do you have a steady sexual partner?	Yes No
C1-11	The last time you had sex, did you or your partner use a condom?	Yes No → C1-13.
C1-12	Do you use condoms every time you have sex?	Yes No
C1-13	Are you currently using any family planning method or contraception?	Yes No

Section C2: HIV testing Now, we are going to ask you questions about HIV testing.		
C2-1	Have you ever been tested for HIV?	Yes No → C3
C2-2	In the last six months, have you been tested for HIV?	Yes No → C3

C2-3	How many months ago was that?	1 month ago 2 or 3 months ago 3-6 months ago 6-12 months ago
C2-4	Do you know your test result?	Yes No

Section C3: Youth-friendly corners

Now, we have two questions about youth-friendly corners.

C3-1	Have you ever heard of a youth friendly corner at the health facility?	Yes → No D
C3-2	In the past 12 months, have you visited a youth friendly corner at the health facility?	Yes No

Section D: JIC (endline only)

Now, we have a few questions about the Join in Circuit (JIC).

D1	Are you currently wearing a wristband from the JIC?	Yes No
D2	Have you participated in a Join-In Circuit run in the last six months?	Yes → D5 No
D3	Have you heard about the Join-In-Circuit?	Yes No
D4	Did any of your friends talk to you about the JIC or things they learned at the JIC? → After question, skip to D12	Yes No
D5	On a scale from 1 to 5, how interesting did you find the JIC? 1 means you didn't find it interesting at all and 5 means you found it very interesting.	Number _____

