3.1 Baseline

The baseline data collection, conducted by a team of 10 trained enumerators divided into 3 groups, lasted about two months from March 16, 2017 to April 11, 2017 and from May 24, 2017 to July 11, 2017 for a total of 52 days. Data collection had to be interrupted during the month of April due to a month-long school break. The survey instrument is attached to this document. The prime reason for the baseline survey—in addition to collecting outcomes before the intervention takes place—was to map the entire friendship network in a given grade (more below).

Once data collection started, the survey team found additional ineligible schools that were either unreachable by car, did not have the targeted grades or were closed. Overall, the survey team managed to conduct a baseline in 98 out of the 102 schools in the treatment group (96% of the target), 28 out of 34 schools in the control 1 category, and 7 out of 34 in control 2. The final sample, thus, consists of 133 schools for the baseline survey. 37 of the schools are in Livingstone and 96 schools in Choma. 19 schools are secondary schools and 114 are primary schools. All students in either grade 6 (if primary school) or grade 11 (if lower secondary school) present on the day of baseline were interviewed for a total of 8,276 students.

Since some instruments are sensitive in nature (more below), we opted to administer self-administered surveys on tablet computers supported by ACASI (audio-assisted computerized assisted self-interview software) technology. Specifically, the survey was loaded unto the tablets and each question was accompanied by an audio file that read out loud the question in the desired language (options were Tonga and English). Students were given headphones for increased privacy. After hearing the question, students were to tap on the relevant answer. Finding the correct answer was facilitated by a) maximizing the number of questions with a vignette or picture or color coded, and by

b) positioning the answers on the left, middle, or right panel of the tablet and have the audio file explain where to find the answer. Two enumerators were present to help and assist in case of confusion or any other problem.

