3.4 Endline

Endline data collection will happen approximately six months after the JIC implementation and will administer the same questions to the same grades identified at baseline. At this point, the endline is scheduled to take place in October 2017.

14 Empirical Analysis

Our primary outcomes of interest are knowledge and self-reported behavior. To assess the degree to which the JIC improved both outcomes, we will create an overall index that standardizes all our outcome variables. This includes all questions in sections B1, B2, B3, and B4. In section C, this includes all questions, but question C1-8. In a second step, we will split the overall index into a self-reported behavior (section A and B), and a knowledge index (section C). In a third step, we will split the index further into the following topics: family planning knowledge (B1), condom knowledge (B2), HIV/Aids knowledge (B3), STIs knowledge (B4), sex behavior (C1), self-reported testing behavior (C2), and self-reported health access behavior (C3). To account for the networked nature

of the trial, we estimate the overall effects, total effects, spillover effects, and direct effects of the JIC on our main index and on our sub-indexes, separately for the three targeting strategies and across targeting strategies.

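### As printed, partner-count item C1-9 has no answer for two partners, and the timing options in C1-2, C1-5 and C2-3 overlap, two of them running past the six-month window of their parent question

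*SAP*

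**What the plan says.** The questionnaire in SAP Section 6.2 is used at baseline and at endline (Section 3.3), and Section 3.4 says the endline puts the same questions to the grades surveyed at baseline.

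- **C1-9** asks "How many sexual partners have you had in the last 12 months". Its answers read "0 1 3-5 More than 5".
- **C1-2** dates the event in C1-1, which asks whether, within a six-month window, "did you visit a health clinic to talk about issues relating to sex or family planning".
- **C1-5** asks "When were you circumcised". Its parent, C1-4, has no time window.
- **C2-3** dates the HIV test reported in C2-2, which also has a six-month window.

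On the index, the opening of Section 4 says "In section C, this includes all questions, but question C1-8", and it then forms sub-indices by topic, among them C1 and C2. All four items therefore count. The intermediate split reads "we will split the overall index into a self-reported behavior (section A and B), and a knowledge index (section C"), which is the reverse of the questionnaire's own section headings. For that reason this point refers only to the overall index and the C1 and C2 sub-indices.

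**The concern.** A closed question must give each respondent one answer that fits. C1-9 does not do so for a student with two partners, and having more than one partner is a behaviour of direct interest to an HIV prevention programme. The timing items let the same event be recorded in either of two categories, and two of them allow an answer that contradicts the question that led to them. Because Section 4 admits whole sections of the questionnaire to the index and states no item coding, these answers would enter the analysis unscreened. Because the endline repeats the questionnaire, a defect present at baseline would recur unless someone corrects it first.

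**Working it through.** The plan gives no figure on this point to reproduce. The check traces the printed options and counts items.

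**1. Coverage of C1-9.** The options cover the counts {0}, {1}, {3, 4, 5} and {6 or more}. The only count not covered is 2. A student with two partners can:
- answer 1, an error of 1 − 2 = −1;
- answer 3-5, an error of 3 − 2 = +1 to 5 − 2 = +3;
- skip, which leaves the item missing.

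Take two students with two partners and one partner, a true difference of 1. The recorded difference is 1 − 1 = 0 if the first answers 1, and 3 − 1 = 2 to 5 − 1 = 4 if the first answers 3-5.

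**2. Timing categories (months ago).**

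| Item | Parent and its window | Printed categories | Shared months | Beyond the window |
|---|---|---|---|---|
| C1-2 | C1-1, six months | 1; 2 or 3; 3-6; 6-12; over 12 | 3 and 6 | 6-12; over 12 |
| C1-5 | C1-4, none | 1; 2 or 3; 3-6; 6-12; over 12 | 3 and 6 | not applicable |
| C2-3 | C2-2, six months | 1; 2 or 3; 3-6; 6-12 | 3 and 6 | 6-12 |

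The overlap at month three is present in all three items. Month six also falls in two categories. Section 3.4 places the endline about six months after the JIC, so that boundary lies near the date of the intervention.

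**3. Weight in the indices.** These are item counts from Section 6.2, with each item counted once; the plan states no weights.
- Section B: 17 + 7 + 12 + 13 = 49.
- Section C: (13 − 1) + 4 + 2 = 18, after removing C1-8.
- Overall index: 49 + 18 = 67.
- All four items in the overall index: 4/67 = 6.0%. C1-9 alone: 1/67 = 1.5%.
- C1 sub-index: C1-2, C1-5 and C1-9 are 3/12 = 25%. C1-9 alone is 1/12 = 8.3%.
- C2 sub-index: C2-3 is 1/4 = 25%.

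**4. Who reaches C1-9.** Only students who answer Yes at C1-6. Section 3.1 reports 114 of 133 baseline schools as primary (114/133 = 86%), surveyed at grade 6. Neither the share answering Yes nor the share with two partners is given, so the number of students affected cannot be computed.

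**5. Need for a baseline match.** The equations in Sections 4.1 to 4.3 contain no baseline outcome, and the covariates listed in footnote 3 include none. A change in endline categories therefore removes nothing that these models use.

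**6. Skip arrows.** As the text reads, the arrows at C1-1 and C1-4 stand beside Yes, so that only students answering No would meet the timing item. Other skip cells are visibly damaged. At B1-9, B1-12, B1-15 and C3-1 the arrow follows Yes but its target follows No. B3-1 shows an arrow to B4 after Yes and no No option, which read literally would send every student who has heard of HIV past the HIV section. D2 has the same form as C1-1 and C1-4 and is sensible. The text at hand cannot settle which reading is right.

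**The case against.** The strongest objection is that this is a matter of text extraction. Options are missing elsewhere in the same tables: A2 shows only Male, and B3-1 has no No. A 2 could have been lost from C1-9 in the same way. This stands as a reason to check the original page. It does not remove the point, because the C1-9 list is otherwise in order and complete, and the timing overlaps are in the wording of the options, not in the layout.

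A second objection is that the effect is small. C1-9 is one of 67 items and is asked of a subset, students may skip uncomfortable questions, enumerators were present to help, and all arms receive the same questionnaire. This also stands, and it confines the point largely to the C1 sub-index. Options beyond six months are mostly redundant, although they do permit contradictory answers.

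A reader might go further and infer that the skips at C1-1 and C1-4 are reversed, so that two of the 12 C1 items hold no valid answers. The documents do not support this, for the reason in step 6. Nor do they show that data were in fact miscollected: the survey ran on tablets ("After hearing the question, students were to tap on the relevant answer"), and the programmed routing and options are not shown. A reader might also suppose that C1-2 is the only item that places a clinic visit after the JIC. It is not, since C1-1 has a six-month window and D6 asks participants about facility visits after the JIC.

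**Conclusion.** The point holds for the answer options as printed. C1-9 has no category for two partners. C1-2, C1-5 and C2-3 have overlapping categories, and C1-2 and C2-3 also exceed the window of their parent question. If fielded as printed, these items add measurement error to 3 of 12 items in the C1 sub-index and 1 of 4 in the C2 sub-index, with little weight in the overall index. The size of the error is unknown. No mechanism for different error between arms is shown, so the support is for lost precision or attenuation on these items and not for a biased comparison of arms. The conclusion assumes that the printed options are those on the original form and the tablet. The skip routing is a query only.

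**What to change.** Before the endline scheduled for October 2017:

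- Check the C1-9 options against the original form and the fielded tablet script. If the gap is real, use 0, 1, 2, 3-5 and more than 5 at endline.
- Make the timing options non-overlapping. For example, use up to 1, 2-3 and 4-6 months in C1-2 and C2-3, with nothing beyond six months. C1-5 has no window and can continue with 7-12 and more than 12.
- Confirm the tablet routing at C1-1, C1-4 and B3-1, and correct it only if it is found to be wrong.
- State in Section 4 how these items are coded in the index.
- If baseline used the printed options, report that baseline C1-9 cannot separate two partners from one or from three to five.

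The cost is an edit to the tablet script and audio files, and a stated departure from the plan to repeat the questions unchanged. These items would no longer match baseline code for code. The planned endline regressions do not need that match, but any descriptive comparison of these items with baseline would have to say so.

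### C3-2 and C1-9 look back 12 months and C2-1 over a lifetime at a six-month endline, so behaviour from before the JIC dilutes their standardised effects, most of all in the C3 sub-index

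*SAP*

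**What the plan says.** Section 3.4 of the SAP states: "Endline data collection will happen approximately six months after the JIC implementation". The questionnaire is the same as at baseline, and "the endline is scheduled to take place in October 2017". Section 3.1 dates the baseline "from March 16, 2017 to April 11, 2017 and from May 24, 2017 to July 11, 2017". Students are chosen for the JIC from lists collected at that visit (section 3.2).

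The opening of section 4 says "we will create an overall index that standardizes all our outcome variables". It then settles which items count: "In section C, this includes all questions, but question C1-8". Testing (C2) and health access (C3) are each analysed as a sub-index. No item coding, weighting or rule limiting items to events after the JIC is given. Footnote 3 lists the individual covariates as A1 to A9. No baseline outcome is among them, although section 3.1 says outcomes were collected before the intervention.

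The survey instrument (section 6.2) uses these look-back periods:

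| Item | Content | Look-back |
|---|---|---|
| C3-2 | youth-friendly-corner visit | 12 months |
| C1-9 | number of sexual partners | 12 months |
| C2-1 | HIV test | lifetime |
| C1-4, C1-6 | circumcision, sexual debut | lifetime status |
| C1-1, C1-3, C2-2 | clinic talk, facility visit, HIV test | 6 months |

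The exact wordings of C3-2, C1-9 and C2-1 are "In the past 12 months, have you visited a youth friendly corner at the health facility", "How many sexual partners have you had in the last 12 months" and "Have you ever been tested for HIV".

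**The concern.** An item can respond to the JIC only through events that happen after it. If the question also counts earlier events, some students answer Yes in either arm whatever the JIC did. A new visit or test by such a student no longer changes the answer, and the extra Yes answers usually enlarge the item's standard deviation. Because the SAP standardises its items, both mechanisms reduce the effect that enters the index.

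This matters most for C3. That sub-index has two items: C3-1 (ever heard of a youth-friendly corner) and C3-2. The only one that measures use of the service has a window twice the planned follow-up. Demand for health services and HIV testing are two of the three aims given for the JIC in section 1, so a weak result there could be read as failure of the tool when part of it comes from the question.

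**Working it through.** The SAP states no power, effect size or item prevalence, so there is no figure of its own to reproduce except the six-month interval. Every prevalence below is an assumption.

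**1. Windows against follow-up.** At exactly six months, 12 − 6 = 6 of the 12 months in C3-2 and C1-9 precede the JIC. Taking baseline as the earliest possible JIC date, the longest possible follow-up to 1 and 31 October 2017 (days / 30.4375) is:

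| Baseline date | to 1 Oct | to 31 Oct |
|---|---|---|
| 16 March | 6.5 | 7.5 |
| 11 April | 5.7 | 6.7 |
| 24 May | 4.3 | 5.3 |
| 11 July | 2.7 | 3.7 |

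For the last schools, 12 − 3.7 = 8.3 to 12 − 2.7 = 9.3 months of the window are pre-JIC. A six-month window also reaches back before the JIC for every school surveyed from 24 May.

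**2. C3-2, independent half-years.** Let p be the control probability of a visit in six months, and p + d the treated probability after the JIC.
- 12-month control probability: 1 − (1−p)² = p(2−p), with SD (1−p)√(p(2−p)).
- 12-month arm difference: (1−p)d.
- Standardised effect: d/√(p(2−p)), against d/√(p(1−p)) for a six-month item.
- Share kept: √((1−p)/(2−p)).

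This gives 0.705 at p = 1%, 0.69 at 10%, 0.67 at 20% and 0.64 at 30%. The raw difference keeps 1 − p, which is 90% at p = 10%. Most of the loss is therefore added variance.

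A second calculation uses a constant visit rate, a 12-month control prevalence of 5% to 40% and a relative effect of 1.5. The standardised share kept is 70% to 66% at six months' follow-up and about 50% to 45% at three.

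**3. C3-2, the other extreme.** If the control students who visit are the same in both half-years and the JIC only adds new visitors, the 12-month and six-month probabilities coincide in each arm. The share kept is then 1, and nothing is lost.

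**4. C2-1.** With prior prevalence a and new testing q regardless of history, P = 1 − (1−a)(1−q) and the raw difference is (1−a)(q1−q0).
- With a = 50% and q = 15% v 25%: 57.5% v 62.5%, so 0.05/0.494 = 0.10 SD. C2-2 gives 0.10/0.357 = 0.28 SD.
- With a from 5% to 70% and q = 5% v 7.5%: the raw difference keeps 95% to 30%, and the standardised effect 70% to 14%.

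**5. C1-4 and C1-6.** These states cannot be reversed, so each new event turns a No into a Yes. The endline difference, (1−a)(q1−q0), equals the difference in new events, and the raw effect keeps 100%. Only the SD grows. With the ranges of the second case in step 4, the standardised effect keeps 72% to 27% unless baseline status is adjusted for.

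**6. C1-9.** This is a banded count, so step 2 does not apply. Earlier partners mainly add variance and leave the mean difference largely alone, apart from the banding.

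**7. Index level.** I take the behaviour index as Section C, as in section 3.3 (the section letters given in section 4 are reversed). It has 12 + 4 + 2 = 18 items. Section B adds 17 + 7 + 12 + 13 = 49, making 67 in the main index. With equal weights, equal true standardised effects and affected items keeping a share k, an index keeps 1 − f(1−k), where f is the affected fraction:

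| Index | f | k = 0.3 | k = 0.7 | k = 0.9 |
|---|---|---|---|---|
| C3 | 1/2 | 0.650 | 0.850 | 0.950 |
| C2 | 1/4 | 0.825 | 0.925 | 0.975 |
| Behaviour | 5/18 | 0.806 | 0.917 | 0.972 |
| Main | 5/67 | 0.948 | 0.978 | 0.993 |

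**The case against.** The best defence is that randomisation balances earlier behaviour in expectation, so each comparison is unbiased for the item as worded. The cost is sensitivity on a minority of items, and different behaviours may reasonably have different windows. This stands, and it rules out several stronger inferences that a reader might draw.

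- **That testing is measured only over a lifetime.** It is not: C2-2 asks about six months and C2-3 dates the test. The C2 sub-index mixes a diluted item with a matched one.
- **That new circumcisions and debuts are hidden.** Step 5 shows that they are not.
- **That service use goes unmeasured in the relevant period.** C1-1 and C1-3 use six months. Neither asks about youth-friendly corners, however, and neither belongs to C3. D6 cannot stand in, because students who did not take part in the JIC are routed past it.
- **That the behaviour effect loses about 30%.** That figure belongs to C3-2 alone and depends on independent half-years. Repeat visitors bring it toward zero.
- **That no change of timetable would help.** A 12-month endline would align C3-2 and C1-9, though not the lifetime item C2-1.

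What the defence does not answer is that C3-2 is the only visit item in a sub-index that the SAP analyses separately, and that neither the scoring nor the covariates remove earlier events.

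**Conclusion.** The mismatch is in the SAP's own text and does not depend on any assumed prevalence: at six months, half of the C3-2 and C1-9 windows is pre-JIC, and more where follow-up is shorter. C2-1 adds lifetime history to the C2 sub-index. The consequence is attenuation, not a spurious effect.

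For C3-2 the standardised loss runs from none (same students in both half-years) to about 30% (independent half-years, low to moderate p), and to roughly half if follow-up is only three months. The C3 sub-index is affected most, the behaviour index modestly (about 81% to 97% kept) and the main index little (about 95% to 99% kept). The index figures assume equal weights and equal true effects. For C1-4, C1-6 and C1-9 the problem is mainly inflated variance. The change is worth making because it is cheap now, and post-JIC visits cannot be separated out of C3-2 once the endline has been collected.

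**What to change.** 1. At endline keep C3-2 and C1-9 as worded. Add to each one follow-up limited to the period since a fixed calendar date matching JIC delivery, asked identically in all arms. Use these versions in the indices. A fixed six-month window is not enough (step 1).
2. Score the C2 index on C2-2, coding as No the never-tested students whom C2-1 routes past it. Report C2-1 separately, since first-ever testing is of interest in itself.
3. Add the baseline value of each outcome to X_ij. This handles C1-4 and C1-6 without new questions, because earlier status is then accounted for. Students absent on the baseline day will lack the value, so state a missing-value rule.

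The cost is two short endline items, which have no exact baseline counterpart, and a few lines of SAP text. The baseline wording of C3-2 and C1-9 can still serve as the covariate for the new versions.
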